### 1.2. Immune response to COVID19.

Death in many patients with COVID19 has been associated with a dysfunctional immune response wherein patients develop cytokine release syndrome (CRS) accompanied by severe ARDS leading to multiorgan failure and subsequent death [2]. In those who have died, persistence of virus in lung tissues coupled with ongoing widespread inflammation has been demonstrated [3]. **Notably, in COVID patients requiring intensive care unit (ICU) support CD4+ and CD8+ T cell numbers have been found to be dramatically reduced (compared with milder disease cases) and the T cells that are present are terminally differentiated and exhausted (characterized by upregulation of markers such as PD-1 and Tim-3) [4-6]. This T cell deficiency may be due, at least in part, to the general immune dysfunction seen in severely ill patients, including elevated levels of suppressor cells (e.g. MDSCs) as well as increased levels of inhibitory cytokines including IL10 in serum [7]. We hypothesize that this T cell deficiency results in failure to clear the virus, and leads to an increased risk of patients requiring mechanical ventilation for ARDS and subsequent death.**

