### **2.4. Exploratory Objectives.**

To study the clinical, immunological and biological effects of partially HLA-matched SARS-CoVSTs to hospitalized COVID19 patients. Outcomes will be compared and described for cancer and non-cancer patients.

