#### **2.4.1 Exploratory end points:**

- a. Expansion/persistence and in vivo effects of infused T cells assessed by a range of T cell measures
- b. Endogenous immune reconstitution/antibody induction
- c. Extended safety of T cell infusion to day 28 and 42 post-infusion
- d. Incidence of Mechanical Ventilation [ Time Frame: Up to 60 days ]
- e. Incidence of advanced ventilation (proning, oscillator or extracorporeal membrane oxygenation or use of inhaled pulmonary vasodilators) [ Time Frame: Up to 60 days ]
- f. Ventilator-Free Days to Day 28 [ Time Frame: Up to Day 28 ]
- g. Organ Failure-Free Days to Day 28 [ Time Frame: Up to Day 28 ]
- h. Incidence of Intensive Care Unit (ICU) Stay [ Time Frame: Up to 60 days ]
- i. Duration of ICU Stay [ Time Frame: Up to 60 days ]
- j. Time to Clinical Failure [ Time Frame: From time of infusion to time of death, mechanical ventilation, ICU admission, or study withdrawal (whichever occurs first, for up to 60 days) ]
- k. Overall Mortality [ Time Frame: Up to 60 days ]
- l. Time to COVID-related Mortality [ Time Frame: Up to 60 days ]
- m. Time to Hospital Discharge [ Time Frame: Up to 60 days ]
- n. Incidence and duration of Supplemental Oxygen [ Time Frame: Up to 60 days ]
- o. Time to Reverse-Transcriptase Polymerase Chain Reaction (RT-PCR) Virus Negativity [ Time Frame: Up to 60 days ]
- p. Serum Concentration of biomarkers of T cell activation

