#### **3.2. Antiviral Activity.**

We will assess the efficacy of SARS-CoV2 specific T cells by comparing the proportion of patients in the treatment arm with those in the control arm (only during the randomized phase of the study) who have a clinical response by day 7 post-randomization (measured as an improvement in their WHO ordinal scale score by 2 or more points or if the patients gets discharged from hospital). When available radiographic response information will also be compared between both groups as well as several other exploratory end-points as listed in section 2.3.

The schedule of monitoring for safety and antiviral activity is demonstrated below.

Table 1. REQUIRED ASSESSMENTS					
	Day-5 to Day -1 (pre-infusion)	Day 0	Days 1-14 (daily)	Days 15 to resolution of treatment-related toxicity (if applicable)	Month 2, 3 and 6
Consent, COVID testing and HLA-typing (research test)	X				
T cell infusion (dose escalation phase) or Randomization  (randomized phase) (research)		X			
History		X	X**	X	X
Acute GVHD and CRS/ICANS evaluation (research) §		X §	X*	X*	
Chemistries: Liver function tests (alkaline phosphatase, bilirubin, AST, ALT), ferritin, DDimer, LDH and CRP §		X	X*/**	X*	
Pregnancy test (research) 	X				
Infusion related toxicity evaluation (research) §		X	X*/**	X*	
Clinical response assessment (WHO ordinal scale)		X	X**	X*	
Chest imaging	X (within 48 hrs of randomization)		X** (at least once post infusion)		
Blood and serum for ancillary laboratory studies (research) 		X	X*/**	X*	X***
CBC with Differential		X	X*/**	X*	X***
Basic Chemistry		X	X*/**	X*	X***

\*At a minimum weekly assessments needed until resolution of all treatment-related toxicities

\*\*Until discharge from hospital

\*\*\*2, 3 and 6 month labs optional and billed to research if performed; history may be obtained via telephone if necessary, off study will be assessed per criteria in [Section 4.3.2](#).

§: Not required for patients randomized to the standard of care arm (control arm)

1: Pregnancy test where applicable (research test)

2: Research procedures beyond that required for usual care - 30-40mls or 6-8 teaspoons may be collected at each time point. Depending on clinical and laboratory responses samples may be collected at additional time points

3: T cells must be infused within 48 hours of randomization.

Research laboratory studies may include:

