#### **4.6. Data Analysis**

All patients who received VSTs infusions or standard of care will be included in the safety analyses. All patients infused with SARS-CoVSTs and finish their 14-day toxicity observation or develop a DLT/tAE before day 14 are considered DLT/tAE evaluable. All efficacy analysis will be based on the intent to treat (ITT) population, defined as eligible and randomized subjects.

Adverse events and corresponding toxicity grades after study treatment will be summarized descriptively by phases then arms. Toxicity information including the type, severity, time of onset, time of resolution, and the probable association with study treatments will be tabulated and summarized. Incidence of DLT/tAE in patients who receive VST infusions defined in [Section 3.1 and 3.4.1](#), will be reported with rates and 95% binomial exact confidence intervals.

Clinical responses will be summarized using rates and 95% binomial exact confidence intervals for the randomized pilot trial phase by arms and compared using Fisher's exact test. Anti-COVID19 efficacy assessed by the WHO ordinal scale will be evaluated every day up to day 14 post-randomization. The assessments will be summarized using descriptive statistics such as medians and ranges. Plots of the assessments over time will be generated for each patient to graphically illustrate the pattern and trend of clinical status. The changes in scales by day 14 post randomization will also be computed; percentages of patients with stable ordinal scale, with worse or improved scales will be summarized by arms.

Clinical exploratory end points (requirement of supplemental oxygen, progression to mechanical or advanced ventilation or ICU, mortality rate, duration on oxygen supplementation, duration of ventilation free, duration of organ failure-free, durations of ICU stay and hospital stay, time to RT-PCR virus negativity) will be summarized in a descriptive nature by arms. Categorical variables will be summarized by frequencies and percentages, and continuous variables will be summarized by means, standard deviations, medians, interquartile ranges. Clinical endpoints will be compared between arms using Fisher's exact tests or Wilcoxon rank sum tests, whichever is appropriate. All statistical tests for clinical exploratory endpoints will be considered exploratory

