Time to clinical failure is defined as the days from VST infusion to date of death, mechanical ventilation, ICU admission, or study withdrawal, whichever occurs first. Patients without those clinical failure events up to 14 days will be considered censored. Time to clinical failure will be estimated in each arm by the Kaplan-Meier method and compared using log-rank tests.

Laboratory data, which include expansion and persistence of infused VSTs, inflammatory markers, biomarkers of T cell activation, will be summarized with appropriate summary statistics. Changes from pre- to post-infusion will be plotted for each patient who receives the VST infusion over time and assessed using paired comparisons when appropriate.

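### The only inferential analysis stated for laboratory change is a before-after comparison in infused patients, which cannot separate a VST effect on immune and inflammatory markers from recovery and background care

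*Protocol*

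**What the plan says.** **Aim.** Section 2.4 states the exploratory objective as "To study the clinical, immunological and biological effects of partially HLA-matched SARS-CoVSTs to hospitalized COVID19 patients". Section 2.4.1 lists, among others, "Endogenous immune reconstitution/antibody induction" and serum biomarkers of T cell activation.

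**Analysis.** The last paragraph of Section 4.6 has two sentences on laboratory data. The first: "Laboratory data, which include expansion and persistence of infused VSTs, inflammatory markers, biomarkers of T cell activation, will be summarized with appropriate summary statistics". The second says that pre- to post-infusion changes will be "plotted for each patient who receives the VST infusion over time and assessed using paired comparisons", with the qualifier that this is done when appropriate. Earlier in the same section: "Clinical endpoints will be compared between arms using Fisher's exact tests or Wilcoxon rank sum tests, whichever is appropriate". The clinical exploratory endpoints listed just before that sentence include no immune, inflammatory or activation marker.

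**Sampling.** In Table 1 (Section 3.2) the § mark means "Not required for patients randomized to the standard of care arm (control arm"). The research blood and serum row has no § mark, so it applies to both arms. The row with liver tests, ferritin, D-dimer, LDH and CRP has it. Section 3.3 lists those same tests on the day of treatment or randomization, and at least weekly while in hospital, with no arm limit, although neighbouring items are marked as treatment-arm only. Section 3.3 also counts study days from randomization in the randomized phase and stops blood and serum collection at day 14 or discharge, whichever comes first.

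**The concern.** The objective is the effect of the VSTs. A paired test in infused patients asks a different question: whether the marker moved after infusion. In an acute infection it may move for other reasons.

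The protocol gives grounds to expect this. Section 4.5 expects half of the controls to meet the response definition by day 7 without VSTs. Section 1.2 ties immune status to severity: in patients needing intensive care, "CD4+ and CD8+ T cell numbers have been found to be dramatically reduced (compared with milder disease cases"). Sections 1.5 and 2.6.4 make the product from donors who have recovered from SARS-CoV-2 infection, so infection itself leaves virus-reactive T cells. Section 2.6.2 allows routine COVID-19 care. One of the endpoints is endogenous recovery by name.

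The risk is that a significant paired change is reported as biological activity of the product when it reflects recovery or background care. The randomized controls, whose research blood is drawn on the same schedule, have no stated role in that inference.

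**Working it through.** **Plan's own figures.** The protocol states no figure for the laboratory analysis. Its nearest figure is the primary power in Section 4.5 (20 per arm, 90% v 50%, one-sided 5% Fisher's exact test). Exact enumeration gives 83.7% against the stated 83%, so the arm size and response rates used below are consistent with the plan.

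**Inputs.**
- Infused patients in the randomized phase: n = 20 (Section 4.5), assuming all are infused and give both samples.
- Natural shift d, in SDs of the within-patient change: not in the documents. Assumed range 0.3 to 1.0.
- VST effect: zero. Test: paired t, two-sided 5%. The protocol says only paired comparisons, so the t-test is also an assumption.

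**Paired test.** The statistic follows a noncentral t with n − 1 = 19 degrees of freedom and noncentrality d√n = d × 4.472. The critical value is 2.093.

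| Assumed shift d | Noncentrality | Significant with no VST effect |
|---|---|---|
| 0.3 | 1.34 | 25% |
| 0.5 | 2.24 | 56% |
| 0.8 | 3.58 | 92% |
| 1.0 | 4.47 | 99% |

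The test is doing its job in detecting a change. The error lies in attributing that change to the VSTs.

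**Between-arm comparison of change.** With complete data, randomization gives both arms the same expected drift, so it cancels and the error rate stays at 5% for any d. For a true difference of e SDs with 20 v 20, the noncentrality is e√(20/2) = e × 3.162 on 38 degrees of freedom. Power is 34% at e = 0.5, 64% at 0.75 and 87% at 1.0. Adjusting for the day-0 value generally helps; no gain is counted here.

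**What discharge does to it.** Inclusion requires SpO2 of at least 92% on room air, so most patients should start at WHO score 3 or 4. Two points better is then score 1 or 2, which is ambulatory, so response is close to leaving hospital. At the planned rates, the patients still in hospital for sampling after day 7 would be about 20 × (1 − 0.90) = 2 treated and 20 × (1 − 0.50) = 10 controls. Those remaining are the non-responders, selected differently by arm. The 5% error rate and the power above do not carry over to that comparison.

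**The case against.** **The protocol does not exclude a between-arm comparison.** The sentence on summary statistics is not limited to infused patients, the paired sentence carries the qualifier on appropriateness, and a SAP not shown here may add more. This stands against any reading that the protocol forbids comparing arms. It does not remove the point: one inferential method is stated for laboratory change, and it does not match the stated objective.

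**Drift is inferred.** Section 1.2 compares severity groups and does not follow patients over 14 days. A reader might infer that the protocol shows these markers move without VSTs in this population; it does not. The 50% control response in Section 4.5 is the strongest support, and it is clinical. The percentages above are therefore illustrative.

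**Comparing arms at day 7 and day 14 could mislead too.** This stands, as the 2 v 10 count shows, and it limits how the fix may be built. It does not favour the paired test, which loses the same discharged patients.

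**Control samples do not cover every marker.** This also stands. Control sampling is scheduled for research blood and serum. For ferritin, D-dimer, LDH and CRP, Table 1 and Section 3.3 disagree, and the documents do not show which is intended.

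**The endpoints are exploratory.** Agreed. The primary comparison, the tAE stopping boundary and the dose-finding rules do not depend on them.

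**Conclusion.** The point holds in a limited form. For inflammatory, activation, virus-specific immunity and antibody measures, the stated paired analysis cannot separate a VST effect from natural course and background care, although the design schedules research blood from randomized controls. Under assumed drifts of 0.3 to 1.0 SD, complete data in 20 infused patients and a two-sided 5% paired t-test, about 25% to 99% of trials with no VST effect would show a significant change.

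The size rests on the assumed drift; the mismatch between objective and method does not. The effect is confined to exploratory mechanistic conclusions, and nothing here supports a doubt about the primary efficacy result or the safety monitoring. Expansion and persistence of infused cells have no control counterpart, so a paired analysis is suitable there.

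**What to change.** 1. **Section 4.6, randomized phase.** For inflammatory, T cell activation, virus-specific immunity and antibody measures, make the analysis a between-arm comparison of change from day 0, adjusted for the day-0 value and labelled exploratory.
2. **Timing.** Use early common post-randomization days on which most patients are still sampled, bearing in mind that infusion may come up to 48 hours after randomization, or fit a model to all in-hospital samples. Report the number sampled per arm and day, and interpret day 7 and day 14 with caution because discharge is expected to differ by arm.
3. **Paired methods.** Keep paired tests for infused-cell expansion and persistence, and keep the per-patient plots as description.
4. **Table 1 and Section 3.3.** Reconcile them on whether liver tests, ferritin, D-dimer, LDH and CRP are required in controls. If they are not measured there, restrict the between-arm analysis to markers from the research blood and serum.

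**Cost.** Analysis wording, plus assay work on control samples that are already scheduled; no new patients or visits. Precision is limited: even with complete data at 20 per arm, power is only 34% for a 0.5 SD difference, and it falls as patients are discharged.

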## 5. REPORTING REQUIREMENTS

### 5.1. Registration

Register all patients with Cell and Gene Therapy Research Coordinator.

The following data will be collected:

- Eligibility
- On study
- Concomitant medication
- Off study
- Response
- Adverse event
- CRS/ICANS Adverse Events (as applicable)
- Death

### 5.2. Drug Toxicity and/or Adverse Reactions.

**5.2.1.** Adverse events will be collected as per [SOP J 02.05.XX](#) and [J02.75.XX](#). Data on adverse experiences/toxicities regardless of seriousness must be collected for documentation purposes only for 14 days after the last dosing of the study drug/biologic

with the exception of all toxicities which were deemed to be related to the infusion and will be followed until resolved.

**5.2.2.** Serious adverse events will be collected and reported as per [SOP J 02.06.XX](#) until 3 months after the last dosing of study drug/biologic.

**5.3. Informed Consent.**

All patients and/or their legal guardian must sign a document of informed consent consistent with local institutional and Federal guidelines stating that they are aware of the investigational nature of this protocol and of the possible side effects of treatment. Further, patients must be informed that no efficacy of this therapy is guaranteed, and that unforeseen toxicities may occur. Patients have the right to withdraw from this protocol at any time. No patient will be accepted for treatment without such a document signed by him or his legal guardian. Full confidentiality of patients and patient records will be provided according to institutional guidelines

**5.4. Clinical Trial Oversight & Monitoring**

This protocol will be conducted in accordance with the Cell and Gene Therapy Monitoring Plan on file with the FDA.

This protocol will be monitored in accordance with the current Data Safety Monitoring Plan of the Dan L Duncan Comprehensive Cancer Center at Baylor College of Medicine.

The conduct of this clinical trial will be evaluated in accordance with the Texas Children's Cancer Center and Center for Cell and Gene Therapy Quality Assurance Policy and Procedure Plan.

## Appendix I

### Appendix I CRS Grading Scale per ASTCT guidelines

Grade	Symptoms
1	
 
• Symptoms are not life threatening and require symptomatic treatment only (e.g. fever, nausea, fatigue, headache, myalgia, malaise)
 

2	
 
• Symptoms require and respond to moderate intervention
 
• Oxygen requirement <40% or hypotension responsive to fluids or
 
• low dose of one vasopressor or Grade 2 organ toxicity
 

3	
 
• Symptoms require and respond to aggressive intervention
 
• Oxygen requirement ≥ 40% or hypotension requiring high dose or multiple vasopressors or
 
• Grade 3 organ toxicity or Grade 4 transaminitis
 

4	
 
• Life-threatening symptoms
 
• Requirements for ventilator support or Grade 4 organ toxicity (excluding transaminitis)
 

5	
 
• Death
 

## Appendix II

### MAGIC Criteria for Staging and Grading of Acute GVHD

Outside of the MAGIC criteria listed in the table below, marrow aplasia as part of GVHD can occur outside of the context of an allogeneic HSCT. So to monitor for marrow aplasia, we will follow CTCAE version 5 for grading of hematologic toxicity. Stopping rules for prolonged or serious marrow aplasia and/or GVHD or other toxicities are detailed above.

Stage	Skin (Active Erythema Only)	Liver (Bilirubin)	Upper GI	Lower GI (stool output/day)
0	No active (erythematous) GVHD rash	<2 mg/dL	No or intermittent nausea, vomiting, or anorexia	Adult: <500 mL/day or <3 episodes/day Child: <10 mL/kg/day or <4 episodes/day
1	Maculopapular rash <25% BSA	2-3 mg/dL	Persistent nausea, vomiting or anorexia	Adult: 500-999 mL/day or 3-4 episodes/day Child: 10-19.9 mL/kg/day or 4-6 episodes/day
2	Maculopapular rash 25-50% BSA	3.1-6 mg/dL		Adult: 1000-1500 mL/day or 5-7 episodes/day Child: 20-30 mL/kg/day or 7-10 episodes/day
3	Maculopapular rash >50% BSA	6.1-15 mg/dL		Adult: >1500 mL/day or >7 episodes/day Child: >30 mL/kg/day or >10 episodes/day
4	Generalized erythroderma (>50% BSA) plus bullous formation and desquamation >5% BSA	>15 mg/dL		Severe abdominal pain with or without ileus or grossly bloody stool (regardless of stool volume).

Overall clinical grade (based on most severe target organ involvement):

Grade 0: No stage 1-4 of any organ.

Grade I: Stage 1-2 skin without liver, upper GI, or lower GI involvement.

Grade II: Stage 3 rash and/or stage 1 liver and/or stage 1 upper GI and/or stage 1 lower GI.

Grade III: Stage 2-3 liver and/or stage 2-3 lower GI, with stage 0-3 skin and/or stage 0-1 upper GI.

Grade IV: Stage 4 skin, liver, or lower GI involvement, with stage 0-1 upper GI.

### Appendix III

[[https://www.who.int/blueprint/priority-diseases/key-action/COVID-19\\_Treatment\\_Trial\\_Design\\_Master\\_Protocol\\_synopsis\\_Final\\_18022020.pdf](https://www.who.int/blueprint/priority-diseases/key-action/COVID-19_Treatment_Trial_Design_Master_Protocol_synopsis_Final_18022020.pdf).]

The ordinal scale is an assessment of the clinical status at a given day. Each day, the worst score from the previous day will be recorded.

#### Ordinal Scale for Clinical Improvement

Patient State	Descriptor	Score
Uninfected	No clinical or virological evidence of infection	0
Ambulatory	No limitation of activities	1
	Limitation of activities	2
Hospitalized Mild disease	Hospitalized, no oxygen therapy	3
	Oxygen by mask or nasal prongs	4
Hospitalized Severe Disease	Non-invasive ventilation or high-flow oxygen	5
	Intubation and mechanical ventilation	6
	Ventilation + additional organ support – pressors, RRT, ECMO	7
Dead	Death	8
